7.2. Screening and Eligibility Assessment

The patients attending the PHT outpatient clinics will be screened to assess whether they have pulmonary arterial hypertension and assessed as to whether they will be able to undertake a 6MWT using the App and then recruited

7.3. Informed Consent

The participant must personally sign and date the latest approved version of the Informed Consent form before any study specific procedures are performed.

Written and verbal versions of the Participant Information and Informed Consent will be presented to the participants detailing no less than: the exact nature of the study; what it will involve for the participant; the implications and constraints of the protocol; the known side effects and any risks involved in taking part. It will be clearly stated that the participant is free to withdraw from the study at any time for any reason without prejudice to future care, without affecting their legal rights, and with no obligation to give the reason for withdrawal.

The participant will be allowed as much time as wished to consider the information, and the opportunity to question the Investigator, their GP or other independent parties to decide whether they will participate in the study. Written Informed Consent will then be obtained by means of participant dated signature and dated signature of the person who presented and obtained the Informed Consent. The person who obtained the consent must be suitably qualified and experienced, and have been authorised to do so by the Chief/Principal Investigator. A copy of the signed Informed Consent will be given to the participant. The original signed form will be retained at the study site and a copy filed in participants medical notes.

7.4. Baseline Assessments

The baseline assessment will be a standard 6MWT which measures resting heart rate and oxygen level at rest, the distance walked over 6 minutes, then the oxygen saturations and heart rate at end of the 6MWT. Prior to the initiation of the test, participants will be asked to download the app onto their personal mobile phones. Participants will also be asked to use the app in its indoor mode, while performing the test in hospital. Participants who are not able to either download the app or use it correctly will be unable to participate. We will be using the BORG questionnaire at the end of both the app test and the hospital 6MWT. The Borg Rating of Perceived Exertion (RPE) is a way of measuring physical activity intensity level. Perceived exertion is how hard a patient feels they are working. It is based on the physical sensations a person experiences during physical activity, including increased heart rate increased breathing rate, increased sweating, and muscle fatigue. Although this is a subjective measure, a person's exertion rating may provide a fairly good estimate of the actual heart rate during physical activity (11). During activity, the patient uses the Borg Scale to assign numbers as to how hard they think they are working. Participants will be provided with the questionnaire at the end of their

Principal Investigator:

[name]

Short Title:

6-APP Study

Ethics Ref:

insert

6MWT and are encouraged to complete the questionnaire by the app or by the hospital physiologist. The physiologists undertaking the test will measure the distance walked using the system website to record the measurement. This way all measurements will be digitally available in one place. At the end of the assessment, participants will be asked to perform a home-based 6MWT within 3 days of the visit and 1 home test per week, or, at least, one per month.

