4. OBJECTIVES AND OUTCOME MEASURES

Objectives	Outcome Measures	Timepoint(s) of evaluation of this outcome measure (if applicable)
Primary Objective O1: To demonstrate that patients are able and willing to use the app for the 6MWT	Percentage of participants who perform app-based home 6MWT	TP 1: 3 months after baseline visit TP 2: 6 months after baseline visit
Secondary Objectives O2: To validate app 6MWT measurements against the hospital 6MWT. O3: To compare the outdoor 6MWT app with the hospital based 6MWT.	Average and variability of the difference in distance as measured by physiologists and the app. Correlation of outdoor 6MWT app parameters with the hospital 6MWT test.	TP 1: at baseline visit TP 2: at 3-month visit TP 3: at 6-month visit TP 1: baseline visit 6MWT compared with following home test TP 2: 3-month visit 6MWT compared with closer home test before or after TP 3: 6-month visit 6MWT compared with closer home test before or after

Principal Investigator:

[name]

Short Title:

6-APP Study

Ethics Ref:

insert

O4: To assess the usability and acceptance of the app and the physicians' website.	Standard usability and acceptance questionnaire to users assessing their use of the app and website, semi structured interviews, analysis of technical logs.	TP 1: at 6 months after baseline visit
Tertiary Objectives	O5: To test whether the 6MWT app can detect changes in 6MWT distance more effectively than the hospital 6MWT, in patients starting advanced therapies.	Comparison of change in 6MWT app measurement with hospital 6MWT measurement, measured before and after initiation of new therapies.

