5. STUDY DESIGN

We propose to evaluate a novel approach to service delivery by monitoring PAH patients using an established m-health system to send 6MWT results to a central server where they can be accessed by the clinical team (Figure 1). The system includes a mobile phone “app” to allow participants to comfortably perform the 6MWT at home (indoors or outdoors). In the outdoor scenario, the app makes use of GPS to track the user’s position. In the indoor scenario it uses the phone’s accelerometer and magnetometer (compass) to count the number of laps over a fixed-length walkway.

[figure not shown]
Figure 1. Diagram of the system

Principal Investigator:
Short Title:

[name]
6-APP Study

Ethics Ref:

insert

Undertaking a 6MWT test within the participant's home environment, using mobile technology to transmit the results via a software application on a mobile phone is appealing as it is likely to be more acceptable to the participant, may provide more consistent and functionally relevant data, and may reduce hospital attendances and healthcare costs. By utilizing biometric collection devices such as a pulse oximeter monitor with Bluetooth capability, telehealth can be used to capture the oxygen saturation levels in the blood from participants and transmit them to a secure server, allowing them to be reviewed by cardiologists and other healthcare professionals.

This study aims to compare the indoor 6MWT, with the hospital performed 6MWT. It will assess the feasibility and acceptance of a mobile phone app as an instrument to measure the 6MWT.

The 6MWT is currently undertaken at every Outpatient appointment, normally at 0- 3-, 6- and 12-month outpatient reviews. The participant would perform a hospital based 6MWT, whilst simultaneously using the indoor version of the app on their own mobile phone at baseline, 3- and 6-month follow up. This will demonstrate to the participant how to use the app, and we will be able to understand whether they are able to use it correctly. It will also allow direct comparison of the standard 6MWT distance measurement with the measurement provided by the app.

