The participant will be then invited to use the app in their local environment, preferably in the outdoor scenario, and the collected information would then be transmitted to the hospital servers where it could be reviewed. The app could be used many times prior to attendance in outpatients, giving the clinicians more detailed information as to the overall functional status of the patient. Participants will be required to perform a test before and after their follow up appointments so that home-based measurements can be compared to hospital-based ones. They will be allowed to do as many tests as they are willing to, preferably once per week and at least each month.

Principal Investigator:

[name]

Short Title:

6-APP Study

Ethics Ref:

insert

In total, we aim to collect 3 indoor hospital-based measurements (baseline, 3- and 6-month) and at least 5 outdoor home measurements, one close to each hospital visit plus one between two visits. The data collected will allow us to understand the usage of the app by participants, validate the indoor measurements and correlate the home measurements with the hospital-based ones.

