7. STUDY PROCEDURES

7.1. Recruitment

Principal Investigator:	[name]	Ethics Ref:	insert
Short Title:	6-APP Study		

Patients undergoing follow up in the PAH clinic will be eligible for participation. They will be approached by a member of the clinical team for consideration and recruited. We will recruit 30 compliant patients to enrol in the study.

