7.6. Discontinuation/Withdrawal of Participants from Study

Each participant has the right to withdraw from the study at any time. In addition, the Investigator may discontinue a participant from the study at any time if the Investigator considers it necessary for any reason including:

- Pregnancy
- Ineligibility (either arising during the study or retrospectively having been overlooked at screening)
- Significant protocol deviation
- Significant non-compliance with study requirements
- Withdrawal of Consent
- Loss to follow up

If participants withdraw from the study, their data until that point will still be analysed, unless deletion of data is requested by the participant (e.g., by withdrawing consent). Any participant that withdraws from the study will be replaced with a new participant. The reason for withdrawal will be recorded in the CRF.

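### Section 10.3 does not say whether consented patients stopped under 7.4 for failing with the app at baseline count in O1; if they are dropped, O1 will tend to overstate ability among consented patients whenever any fail

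*Combined protocol and SAP*

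**What the plan says.** Section 4 states the primary objective: "To demonstrate that patients are able and willing to use the app for the 6MWT". The outcome is a percentage of participants. Section 10.3 counts a participant as a success if at least one home test is done between baseline and 3 months and, separately, between baseline and 6 months. It makes these two percentages the study's chief yardstick of success. Its only stated exclusion from the data is withdrawal of consent.

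Four other sections determine who can enter that percentage:

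- Section 7.2: before recruitment, patients are "assessed as to whether they will be able to undertake a 6MWT using the App and then recruited".
- Section 7.3: consent is signed "before any study specific procedures are performed".
- Section 5: of the baseline hospital walk with the app, "we will be able to understand whether they are able to use it correctly".
- Section 7.4: of that same baseline step, "Participants who are not able to either download the app or use it correctly will be unable to participate".

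Section 7.1 adds: "We will recruit 30 compliant patients to enrol in the study". Section 7.6 adds: "Any participant that withdraws from the study will be replaced with a new participant". Neither 7.6 nor 10.3 says whether a patient stopped under 7.4 is a withdrawal, or whether that patient counts in O1.

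**The concern.** Ability to use the app is part of what O1 is meant to show, and 7.4 also makes it a condition for staying in the study. A patient who has consented, tries the app at baseline and cannot work it is direct evidence on the primary objective. If that patient leaves the denominator, the evidence leaves the primary result.

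Two competent analysts could also report different primary percentages from the same data, one keeping these patients and one dropping them, and each could cite the protocol in support. If nobody tallies the failures as they happen, the fuller figure may not be recoverable later.

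**Working it through.** **Inputs.** The documents give a target of 30 (7.1, 10.2) with no sample size calculation. They give no expected O1 percentage, no success threshold and no number of baseline app failures, so there is no plan figure to reproduce. Three quantities are therefore assumed:

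- x = participants who do at least one home test;
- f = consented patients stopped under 7.4;
- k = how many of those f would have managed a home test had they been allowed to try.

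**Step 1: which reading of the text.** Section 7.4 calls these patients participants, and 10.3 uses the data of all participants except those who withdrew consent. Read literally, that could keep them. But 7.4 says they cannot participate, and 7.1 aims for 30 compliant patients. Together these make exclusion the more natural reading. It is an ambiguity, not a stated exclusion.

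**Step 2: failures replaced, so that 30 patients pass the baseline step.** Dropping failures gives x/30. Counting them as non-performers gives x/(30 + f). With x = 27 and exact (Clopper-Pearson) 95% intervals:

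| f (assumed) | Failures counted as non-performers | 95% CI | Difference from 90.0% |
|---|---|---|---|
| 0 | 27/30 = 90.0% | 73.5 to 97.9 | 0 |
| 1 | 27/31 = 87.1% | 70.2 to 96.4 | 2.9 points |
| 3 | 27/33 = 81.8% | 64.5 to 93.0 | 8.2 points |
| 5 | 27/35 = 77.1% | 59.9 to 89.6 | 12.9 points |

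With f = 3 and other assumed x: 24/30 = 80.0% becomes 24/33 = 72.7% (54.5 to 86.7), and 30/30 = 100% becomes 30/33 = 90.9% (75.7 to 98.1).

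**Step 3: failures not replaced, so that 30 is the number consented.** Dropping failures gives x/(30 − f); counting them gives x/30. With f = 3 and x = 24, 24/27 = 88.9% becomes 24/30 = 80.0%, a difference of 8.9 points. The direction is the same and the size is similar.

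**Step 4: is the direction certain?** Counting failures as non-performers gives a lower bound, because 7.4 stops them from attempting a home test. Had they been allowed, the percentage would be (x + k)/(30 + f). This is below x/30 exactly when k/f < x/30, that is, when failures would have done worse at home than those who passed. With x = 27 and f = 3:

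- k = 0: 27/33 = 81.8%
- k = 1: 28/33 = 84.8%
- k = 2: 29/33 = 87.9%
- k = 3: 30/33 = 90.9%

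The conditional 90.0% is too high for k = 0, 1 or 2, and slightly too low only if all three would have succeeded. Overstatement is therefore a likely tendency, not a mathematical certainty.

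**The case against.** The strongest reply is that restriction to app-capable patients is declared design. Section 6.2 requires a compatible smartphone that the patient can use, 6.3 excludes those who cannot use one, and 7.2 assesses app ability before recruitment. On this view 7.4 only confirms eligibility in practice, failures will be few or none, and some download failures will simply mean an incompatible phone. This stands in part. Phone incompatibility is ineligibility under 6.2 and should not be scored as inability, and with no failures there is no effect. But 6.2 and 6.3 speak of using a smartphone, not this app, and 7.4 provides for failures after consent.

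A second reply is that 10.3 read literally already keeps these patients. That reading is available. If it is the intention, a sentence should say so, because 7.4 points the other way.

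A third is that scoring patients as non-performers when the protocol bars them from trying partly measures the bar itself. This also stands. It is why the figure must be labelled a lower bound and shown beside the conditional percentage.

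A fourth is that the illustrated shift at f = 3, to 81.8%, lies inside the conditional interval of 73.5 to 97.9. That is true, but the interval describes sampling error among patients who passed; it does not cover a change in who is counted.

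A reader might go further and infer that O1 does not test ability at all. The documents do not support that. The baseline step is passed in hospital, with physiologists present, in indoor mode. At home, patients are invited to "use the app in their local environment, preferably in the outdoor scenario", where the app relies on GPS. Someone can pass at baseline and still fail alone at home, so O1 keeps part of its meaning.

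**Conclusion.** The point holds as an unsettled denominator whose more natural reading conditions the primary result on part of what it is meant to show. O1 would then be a valid figure for home use among patients already shown able to use the app under supervision, but not for ability among those who consented.

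The size cannot be known from the documents; every count above is assumed. The direction rests on at least one patient failing at baseline and on failures being less likely than the others to manage a home test. A reader might infer that a single failure guarantees overstatement; step 4 of the working shows that it does not. A reader might also infer that the study's conclusion could flip. With an exploratory design (10.2) and no O1 threshold, no decision changes; only the estimate and its description do.

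Selection under 6.2, 6.3, 7.1 and 7.2 comes earlier and remains whichever denominator is used. The documents do not show which step selects most. Severity is minor to moderate.

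**What to change.** In 10.3, define the O1 denominator at both 3 and 6 months as all consented, eligible patients who attempted the baseline app step. Include those stopped under 7.4 and those replaced under 7.6. Keep the existing exclusion of patients who withdrew consent, but report how many there were.

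Count baseline app failures as non-performers and label the result a lower bound. Show beside it the percentage among those who passed the baseline app step.

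From the start of the study, tally app failures at screening (7.2) and at baseline (7.4) with reasons, separating phone incompatibility from inability to use the app. State that the selection under 6.2, 6.3, 7.1 and 7.2 remains in both figures.

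The cost is a few sentences of wording and a simple log, with no extra patients or visits. The downside is that two figures must be reported and the headline percentage may be lower.

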7.5. Subsequent Visits

The participants will be followed up as per the normal outpatient protocol at 3 and 6 months. At all the appointments they will perform a standard hospital based 6MWT, which will again document resting heart rate and oxygen saturations, the distance the participant walks in 6 minutes and their heart rate and oxygen saturations at the end. Participants will be asked to use the app while performing the test. The BORG questionnaire will be also presented at the end of the test.

After the test, if no home 6MWT was performed within 3 days before the visit, participants will be reminded to perform a home test within the following 3 days. In addition, participants will be reminded to perform 6MWTs at home once per week, or at least once per month. At the end of the study, all participants will be asked to complete a usability and technology acceptance questionnaire and a group of randomly chosen 5 to 10 patients will be asked to attend a short interview about the use of the app.

7.6. Discontinuation/Withdrawal of Participants from Study

Each participant has the right to withdraw from the study at any time. In addition, the Investigator may discontinue a participant from the study at any time if the Investigator considers it necessary for any reason including:

- Pregnancy
- Ineligibility (either arising during the study or retrospectively having been overlooked at screening)
- Significant protocol deviation
- Significant non-compliance with study requirements
- Withdrawal of Consent
- Loss to follow up

If participants withdraw from the study, their data until that point will still be analysed, unless deletion of data is requested by the participant (e.g., by withdrawing consent). Any participant that withdraws from the study will be replaced with a new participant. The reason for withdrawal will be recorded in the CRF.

7.7. Definition of End of Study

The end of study is the date of the 6-month follow up appointment for the last participant.

Principal Investigator:

[name]

Short Title:

6-APP Study

Ethics Ref:

insert

8. IDENTIFICATION & DESCRIPTION OF THE DEVICE

8.1. Description of the Device

The app used in the study, called "SMWT" is a smartphone "app", and is a software device. Its main purpose is to measure the walked distance in a timed walk. In the "outdoor mode", the app makes use of GPS to track the user's position and compute the distance. In the "indoor mode" it uses the phone's compass to count the number of laps over a fixed-length walkway. The app also collects blood saturation and pulse samples from commercially available pulse-oximeters, connected to the phone via a wireless link. The app is available, free of charges, on common "app stores" (Google Play Store and Apple iTunes) and is currently not distributed as a medical device but as a research prototype.

The app is able to retrieve data from two commercial pulse-oximeters: Creative Medical PC-68B and Nonin Onyx II, both certified as medical devices in Europe and United States. The validation of the pulse-oximeters is not object of this research.

8.2. Device Safety

The app is being tested in relation to its reliability and the accuracy of distance estimation.

In the "indoor mode", from 46 tests in lab and with actual patients, the app has an average absolute error of 5.58 m and a maximum of 21.46 m, which is below the threshold that is considered clinically relevant. In the "outdoor" mode, from 24 tests performed in lab, the average error is 11.23 m and the maximum 27.19 m, both still not clinically significant.

There are no safety risks associated to use of the app.

Volunteers are also being involved in technical testing and assessing usability and long-term acceptance.

8.3. Device Accountability

The production of the software app is responsibility of the Department of Engineering Science of the University of Oxford.

9. SAFETY REPORTING

The study is low risk however, in the event of an adverse event (AE) or serious adverse event (SAE) occurring to a participant this would be reported to the REC and MHRA in the annual report.

9.1. Definitions

Adverse Event (AE)	Any untoward medical occurrence, unintended disease or injury or any untoward clinical signs (including an abnormal laboratory findings) in participants, users or other persons whether or not related to the
--------------------	--

Principal Investigator:

[name]

Short Title:

6-APP Study

Ethics Ref:

insert

	investigational medical device. This includes events related to the investigational device or comparator, events related to the procedures involved (any procedure in the protocol). For users or other persons this is restricted to events related to the investigational medical device.
Adverse Device effect (ADE)	An adverse event related to the use of an investigational medical device. This definition includes any events resulting from insufficient or inadequate instructions for use, deployment, implantation, installation, or operation, or any malfunction of the investigational device. This definition also includes any event resulting from user error or form intentional misuse of the investigational device.
Serious Adverse Event (SAE)	
An adverse event that:
 
 • Led to death • Resulted in serious deterioration in the health of the subject that: 
 ○ resulted in a life-threatening illness or injury ○ resulted in a permanent impairment of a body structure or a body function ○ required in-patient care or prolongation of hospitalisation ○ resulted in medical or surgical intervention to prevent life-threatening illness or injury or permanent impairment to a body structure or a body function. 
This includes device deficiencies that might have led to a serious adverse event if:
 
 a) suitable action had not been taken or b) intervention had not been made or c) circumstances had been less fortunate. 
These are handled under the SAE reporting system.
 
Planned hospitalisation for a pre-existing condition, or a procedure required by the trial protocol, without serious deterioration in health, is not considered a serious adverse event.

Serious Adverse Device Effect (SADE)	
Any untoward medical occurrence that can be attributed wholly or partly to the device, which resulted in any of the characteristics of a serious adverse event as described above.
 
Unanticipated Serious Adverse Device Effects (USADE)

Principal Investigator:

[name]

Short Title:

6-APP Study

Ethics Ref:

insert

	Any serious adverse device effect which, by its nature, incidence, severity or outcome, has not been identified
Device deficiency	
Inadequacy of a medical device with respect to its identity, quality, durability, reliability, safety or performance. Device deficiencies include malfunctions, use errors and inadequate labeling.
 
Device deficiencies that did not lead to an adverse event, but could have led to a medical occurrence if suitable action had not been taken, or intervention had not been made or if circumstances had been less fortunate

User error	
Act or omission of an act that results in a different medical device response than intended by the manufacturer or expected by the user. Use error includes slips, lapses and mistakes. An unexpected physiological response of the subject does not itself constitute a use error.

Severity definitions

The following definitions will be used to determine the severity rating for all adverse events:

Mild: awareness of signs or symptoms, that does not interfere with the subject's usual activity or is transient that resolved without treatment and with no sequelae.

Moderate: a sign or symptom, which interferes with the subject's usual activity.

Severe: incapacity with inability to do work or perform usual activities.

